9.4.4 Secondary Efficacy Variables Analysis

All secondary efficacy endpoints will be tabulated by treatment groups on the mITT and PP populations.

For the secondary endpoint TLUS, defined as the interval beginning with the first dose of study drug and ending with the last unformed stool passed, summary tables will be presented along with p-values using appropriate statistical method.

For microbiological cure rate, summary tables will include number and percentage of subjects in each category; differences between groups (test vs placebo, reference vs placebo, and test vs reference) will be derived along with the 95% CIs for the difference using the Z-test for proportion to test the difference between the treatment groups; the Yates's correction will be applied for the calculation of 95% CIs.

For variables related to number of formed and number of unformed stools by study day, summary tables will include number and percentage of subjects with 0, 1, 2 ... etc. number of stools by treatment group and time point. Stools occurred on Day 1 prior to receiving first dose of study drug will be included in the bowel movement at baseline; number of stools on Day 1 will include only those occurred on Day 1 after the first dose of study drug.

9.5 Analysis of Safety Parameters

All adverse events (AEs) and treatment-emergent AEs (TEAEs) reported during the study will be summarized/reviewed in order to assess safety. Safety will be evaluated by incidence of TEAEs including incidence of selected TEAEs of special interest, incidence of SAEs; TEAEs by relationship to study drug and intensity; and TEAEs leading to discontinuation. Observed results and change from baseline in clinical laboratory tests, vital signs, and physical examinations will be tabulated by treatment group.

MedDRA (using the latest available version) will be used to classify all AEs with respect to SOC and preferred term. All safety summaries will be performed on the safety analysis set by treatment group without inferential statistics.

Total extent of exposure to study drug will be measured by total number of tablets taken and duration of exposure calculated as date of last dose minus date of first dose plus 1. Study drug compliance (%) will be calculated as number of tablets taken divided by number of tablets expected to take multiplied by 100. Subjects are considered to have good compliance if the compliance (%) is within the range of ~75% to ~125%, corresponding to 7 to 11 doses.

9.6 Sample Size Calculation

The sample size calculation for this study is based on the published literature ([CDER statistical review of NDA submission 21-361](#)) and FDA's current guidance ([FDA Guidance, 2004](#)) on the clinical endpoint bioequivalence study of Rifaximin 200 mg. [REDACTED]

Thus, approximately 618 patient(s) [REDACTED] will be enrolled and randomized [REDACTED] for Test vs. Reference vs. Placebo [REDACTED]

█ the overall dropout rate from the randomized patient population to mITT population does not exceed 15%. █
█ the PP population when the lower and upper 90% CI falls within [-0.20, +0.20].

9.7 Handling of Drop-outs and Discontinuations

█
█
█
█
█

Missing data for other assessment (eg, safety assessment or baseline assessment) will not be imputed. However, for the purpose of summary, AEs with missing relationship to study drug assessment will be counted as “related”; AEs with missing intensity assessment will be counted as “severe”. Missing intensity and relationship will be presented as is on the individual subject data listing.

9.8 Interim Analyses

No interim analysis is planned for this study.

9.9 Data Monitoring Board

A formal data monitoring board for safety and efficacy during the study will not be required.

10. Study Administration

10.2 Local Ethics Committee (LEC)/Institutional Review Board (IRB) Approval

GCP requires that the clinical protocol, any protocol amendments, the Investigator's Brochure, the informed consent form, and all other forms of subject information related to the study and any other necessary documents be reviewed by an LEC/ IRB.

It is required that a valid LEC/IRB approves in writing the conduct of this clinical study, together with the Investigator's informed consent document, prior to study initiation.

The trial protocol was developed in accordance with the Declaration of Helsinki, the ICH Guidance on GCP.

In performing this study, both the Investigator and Sponsor endorse, as a minimum, the standards for conduct of clinical research activities as set forth in the Declaration of Helsinki, ICH guidelines and local country laws and regulations.

The Investigator will submit the protocol and informed consent for LEC/IRB acceptance. This will be appropriately documented. The LEC/IRB should be asked to give its acceptance in writing. The names and qualifications of the members of the review committee will be recorded and submitted to the Sponsor, together with the written acceptance for the conduct of the study. The members of the LEC/IRB accepting must be independent of the Sponsor and the Investigator. The written acceptance should consist of a completed LEC/IRB acceptance form or written documentation from the containing the same information.

Until written acceptance by the LEC/IRB has been received by the Sponsor, no subject may undergo any procedures solely for the purpose of determining eligibility for this study. Protocol amendments must also be reviewed and accepted by the LEC/IRB and written acceptance from the committee or at least the chairperson (or a designated committee member) must be received by the Sponsor before implementation. This written approval will consist of a completed LEC/IRB acceptance form or written documentation from the LEC/IRB containing the same information.

10.3 Ethical Conduct of the Study

The study will be conducted in accordance with the protocol, all ICH and GCP regulations governing clinical study conduct; ethical principles that have their origin in the Declaration of Helsinki and all applicable local laws and regulations. The investigator must assure that the study is conducted in accordance with the provisions as stated in the US FDA regulations and complies with prevailing local laws and customs.

10.4 Subject Information and Consent

The investigator or designee will explain the nature of the study to the subject, and answer all questions regarding this study, prior to obtaining informed consent.

The Investigator or designee will obtain informed consent from each subject enrolled in the study, in accordance with the Declaration of Helsinki, the current version of the ICH guidelines and the laws and regulations of the country in which the investigation is being conducted. In addition, study subjects must sign a HIPAA authorization, where required.

The LEC/IRB must accept the informed consent document to be used by the Investigator. It is the responsibility of the Investigator to assure that the subject has signed the informed consent form before any activity or treatment is undertaken. This includes, but is not limited to, the

performance of diagnostic or therapeutic procedures and the administration of the first dose of study medication.

10.5 Subject Confidentiality

Adequate records have to be maintained for the study, including subject medical records, eCRFs, laboratory reports, worksheets, nursing notes, signed informed consent forms, product forms, SAE forms, and information regarding subject discontinuation and reasons for discontinuation. The confidentiality of each record with subject identification is to be guaranteed by the clinical investigator.

This study protocol and other study documents contain trade secrets and commercial information that is privileged and confidential. Such information is not to be disclosed unless required by laws or regulations. The investigator agrees to use this information only in conducting this study and is not allowed to use it for other purposes without written consent from the Sponsor. Results obtained from this study are the property of the Sponsor.

10.6 Study Monitoring

For protocol monitoring and compliance, a site initiation visit will be held prior to subject enrolment. The protocol, eCRF, IWRS entries, study treatment supplies, and study procedures will be explained in detail.

The purpose of monitoring is to verify the rights and well-being of human subjects are protected; that study data are accurate, complete, and verifiable with source data; and that the study is conducted in compliance with the protocol, GCP, and the applicable regulatory requirements.

A monitor assigned by the designated CRO will conduct regular site visits for the purpose of study monitoring.

The investigator must agree to allow the study monitor and authorized representatives of the designated CRO or the Sponsor to inspect all eCRFs and corresponding source documents (e.g., original medical records, subject records and laboratory raw data); to allow access to the clinical supplies, dispensing, and storage areas; and to agree to assist with their activities, if requested. The investigator should provide adequate time and space for monitoring visits.

The monitor will query any missing or spurious data with the investigator, which should be resolved in a timely manner. A visit log will be maintained to record each visit, the reason for the visit, the monitor's signature, and the investigator's or designee's confirmation signature.

10.7 Case Report Forms and Study Records

Subject source documents are the physician's records maintained at the study site. The information collected on the eCRF must match those charts. In some cases, a portion of the source for a given subject may be the eCRF.

The eCRF data will be collected electronically. Instructions for entering data via internet will be provided in the eCRF Completion Guidelines and training will be provided to the study site staff prior to initiation of the site.

Periodically, the Monitor or other authorized Sponsor personnel will visit the study site for the purpose of comparing the data on the eCRF with the source documents. The Investigator agrees to make source documents available for this purpose. The eCRF should be completed as soon as possible after the data are available.

A minimum of the following set of documents will be received by the CRO prior to the initiation of the study:

1. Fully executed protocol
2. Debarment Letter
3. Completed and signed FDA Form 1572
4. Current curricula vitae, signed and dated for the Investigator and each Sub-Investigator named in the FDA Form 1572 (current within 2 years)
5. Current medical licenses of the Investigator and Sub-Investigators named in FDA Form 1572
6. Documentation of "No Objection" to proceed from the local regulatory agency, where ever applicable.
7. Documentation of LEC/IRB approval of this study protocol, Investigator and informed consent forms
8. Current LEC/IRB membership list or roster and EC SOPs
9. Financial Disclosure Statement for the Investigator and each Sub-Investigator named in FDA Form 1572
10. Sites Clinical Laboratory Head's current (within 2 years) curricula vitae and normal reference ranges of laboratory parameters
11. Fully executed Clinical Trial Agreement

10.8 Data Monitoring Committee

Not applicable.

10.9 Protocol Violations/Deviations

When a variation from the protocol is deemed necessary for an individual subject, the Investigator or other physician in attendance must contact the Sponsor's Medical Monitor or sponsor representative through the CRO representatives.

Such contact must be made as soon as possible to permit a decision as to whether or not the subject is to continue in the study. The deviation from the protocol will be authorized only for that subject.

All deviations related to study inclusion and exclusion criteria and significant deviations to subject management and protocol procedures must be documented on the appropriate eCRF.

Major protocol deviations/violations will include, but are not limited to, the following:

- Did not meet any critical inclusion/exclusion criteria which may impact the assessment of treatment efficacy.
- Did not receive randomized treatment (i.e., the actual treatment is not randomized treatment).
- Use of prohibited concomitant medications (e.g., prescription or OTC anti-diarrheal drug product, NSAIDs [with the exception of acetaminophen and paracetamol] or opioid analgesics).
- Did not meet the drug compliance of taking ≥ 7 to ≤ 11 doses.
- Did not come for Visit 3 within the visit window period of 24 to 72 hours of last dose.

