5.8 Concomitant Medications and Therapy

All concomitant medications and therapies used during the trial will be documented in the eCRF including name of the medication, date of administration and its duration, and indication for use.

Over-the-counter (OTC) anti-diarrheal medications, NSAIDs (with the exception of acetaminophen and paracetamol) and opioid analgesics are prohibited during the study. For further detail, please refer to Section 4.3 of the protocol. Use of prohibited concomitant medications will be considered a major protocol deviation and the subjects will be withdrawn from the study; and will be excluded from the per protocol (PP) analysis set.

6. Study Procedures

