### 3. STUDY OVERVIEW

#### 3.1 Study Design

This is a randomized, double blind, placebo controlled, parallel design, multicenter bioequivalence study, designed to demonstrate

- i. Bioequivalence of Test (Rifaximin 200-mg Tablets) to Reference (Xifaxan® 200-mg Tablets) in the treatment of Travelers’ Diarrhea.
- ii. Superiority of test and reference products over placebo with respect to the clinical cure rates within a period of 24 to 48 hr. from the time of last dose, in the treatment of TD, using the mITT population with LOCF.

Approximately six hundred eighteen (618) adult, non-indigenous travelers with naturally acquired acute diarrhea will be enrolled up to 40 sites. Subjects will be participating in the study for approximately 7 days and will be randomized  to receive rifaximin 200-mg tablets, Xifaxan 200-mg tablets, or placebo tablets, TID for 3 days, beginning not more than 72 hours after the onset of diarrhea.

The scheduled study visits will include:

- Visit I: Screening, Randomization and Treatment Visit [Day 1 to Day 4]
- Visit II: Telephone Visit [Day 3]
- Visit III: Test of Cure Visit [>24 hrs from the time of last dose]

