## 4. STUDY ENDPOINTS

### 4.1 Efficacy Endpoints

#### 4.1.1 Primary Efficacy Endpoint

**As per protocol**, the primary efficacy endpoint is clinical cure rate on TOC Visit (Study Day 5, 6 or 7). Clinical cure is defined as either of the following:

- No stools or only formed stools within a 48 hour period and no fever, with or without other enteric symptoms, OR
- No watery stools or no more than two soft stools passed within a 24 hour period with no fever and no other enteric symptoms except for mild excess gas/flatulence.

In addition, clinical deterioration by Study Day 5 or failure to achieve formed stool in  $\leq 3$  days (i.e., within 72 hrs from the time of first dose) is a clinical failure.

**As per FDA's OGD guidance**, the primary endpoint is clinical cure at the test of cure (TOC) visit on study Day 5, *with a window period of +/- one day*. In line with OGD, the protocol was designed such that the TOC visit should occur 24 to 72 hours after the last dose of study drug administration. After the study initiation, it was observed that some subjects were not able to complete the TOC visit within the above defined window period and a protocol deviation was filed to redefine the cut-off time point for evaluation of primary efficacy endpoint. Since, all the subjects were completing their diaries until the TOC visit and all the sites entered all diary data in the EDC that includes the data beyond the upper limit of window period for some subjects, decision was taken to consider 24 to 48 hour data for efficacy analysis. Thus, clinical cure rate was assessed on Visit-3 using subject's diary data from 24 to 48 hour period from the time of last dose when the drug is administered 3 times a day (TID) for 3 days in subjects with Travelers' Diarrhea (TD). Accordingly, clinical cure is re-defined as either of the following:

- No stools or only formed stools within a 48 hour period **from the last dose** with no fever, and with or without other enteric symptoms, OR
- No watery stools or no more than two soft stools passed within a 24 hour period **from the time of last dose** with no fever and no other enteric symptoms except for mild excess gas/flatulence.

This above decision was taken to standardize the data to be used for efficacy analysis and therefore there is no impact on the quality, safety & integrity of data due to the following reasons-

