#### **8.6 Protocol deviations**

The following describes the protocol deviations that relate to statistical analyses or Per-protocol population.

All deviations related to study inclusion and exclusion criteria and significant deviations to subject management and protocol procedures must be documented on the appropriate eCRF. Major protocol deviations/violations will include, but are not limited to, the following:

- Did not meet any critical inclusion/exclusion criteria which may impact the assessment of treatment efficacy.
- Did not receive randomized treatment (i.e., the actual treatment is not randomized treatment).
- Use of prohibited concomitant medications (e.g., prescription or OTC anti-diarrheal drug product, NSAIDs [with the exception of acetaminophen and paracetamol] or opioid analgesics).
- Did not meet the drug compliance of taking  $\geq 7$  to  $\leq 11$  doses.
- Did not come for Visit 3 or did not provide efficacy data for 24 hour to 48 hour period after the last dose.

A list of protocol deviations will be compiled prior to database closure for the primary analysis

and be updated prior to the analysis. The deviations will be listed on randomized population and also will be summarized on randomized population by treatment group.

[figure not shown]
Further, all the protocol deviations will be manually reviewed by the medical monitor of the study to determine whether any deviation is significant with respect to per-protocol population. Such deviations which may affect the treatment evaluation would be declared as “significant” protocol deviation by the medical monitor, and consequently these subjects will also be excluded from the per-protocol population for the primary efficacy analysis, in addition to above mentioned protocol deviations.

The medical monitor will send the significant protocol deviations to Biostatistics team in an excel sheet through email before DB lock. All these significant protocol deviations will also be submitted to regulatory in the form of XPT file along with the protocol deviations captured in the eCRF. The additional list of these protocol deviations will be prepared with respect to per-protocol population criteria and will be listed on randomized population by treatment group.

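### As the visible text reads, prohibited medication taken after the primary outcome is already scored still removes the subject from the per-protocol (PP) bioequivalence set

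*Protocol*

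**What the plan says.** **Medication rule.** Protocol 5.8 states that OTC anti-diarrheals, NSAIDs (with stated exceptions) and opioids "are prohibited during the study". It continues: "Use of prohibited concomitant medications will be considered a major protocol deviation and the subjects will be withdrawn from the study", and such subjects "will be excluded from the per protocol (PP) analysis set". Protocol 10.9 lists the same event among major deviations ("Use of prohibited concomitant medications (e.g., prescription or OTC anti-diarrheal drug product, NSAIDs"), and SAP 8.6 repeats it. None of the three gives an end time. SAP 8.6 then has the medical monitor review all deviations. For those found significant, "consequently these subjects will also be excluded from the per-protocol population for the primary efficacy analysis, in addition to above mentioned protocol deviations". That review adds exclusions; nothing visible lets it restore a subject.

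**Scoring window.** In SAP 4.1.1 a "decision was taken to consider 24 to 48 hour data for efficacy analysis", and cure is redefined relative to the last dose. SAP 7.5.1 uses the same window.

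**Visit 3.** Protocol 6.5 places it 24 to 72 h after the last dose. SAP 3.1 gives only a lower limit, "Test of Cure Visit [>24 hrs from the time of last dose", and SAP 4.1.1 records that some subjects missed the protocol window.

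**Neighbouring deviation.** In the same SAP 8.6 list, the visit item has been tied to the new window: "Did not come for Visit 3 or did not provide efficacy data for 24 hour to 48 hour period after the last dose". The medication item has not.

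**Role of the set.** Both documents make PP the primary set for test versus reference.

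**The concern.** The study lasts longer than the period in which the primary outcome is scored, and the exclusion follows the study rather than the scoring. An analgesic or anti-diarrheal first taken after scoring closes cannot change a diary outcome that is already fixed. Removing the subject therefore discards a valid primary observation without protecting the comparison.

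The loss need not be neutral. Subjects who are still ill when scoring closes are plausibly the likeliest to take something afterwards. If so, observed failures leave both active arms. When cure rates are high this pulls the arms together, which is the wrong direction for an equivalence claim. Cured subjects can be lost too, for example one who takes ibuprofen on the day of a late visit.

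**Working it through.** **1. Timeline after the last dose**

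| Event | Time | Source |
|---|---|---|
| Primary diary scoring ends | 48 h | SAP 4.1.1, 7.5.1 |
| Visit 3, Protocol | 24 to 72 h | Protocol 6.5 |
| Visit 3, SAP | more than 24 h, no upper limit | SAP 3.1, 3.8 |
| Prohibition ends | end of study | Protocol 5.8 |

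The exposed gap is nil if Visit 3 falls by 48 h, at most 72 − 48 = 24 h inside the Protocol window, and unbounded under the SAP.

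One edge case remains. Clinical deterioration by Study Day 5 is also a failure. If dosing ends on Day 3, the end of Day 5 can fall some hours after the 48 h point. Primary scoring therefore closes at the later of the two times.

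**2. Sample size.** The plan's 618 cannot be reproduced, because the assumed cure rates and PP size are blacked out. With the 1:1:1 heading and 15% dropout in the SAP's sample size section: 618/3 = 206 per arm, and 206 × 0.85 = 175.1. I use 175 per arm as an assumed PP size.

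**3. Model.** Assume true cure of 0.60 (test) and 0.80 (reference), which is exactly at the margin. A share q of failures, and no cures, is dropped in both arms:

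- P_T = 0.60/[0.60 + 0.40(1 − q)], N_T = 175 × that denominator
- P_R = 0.80/[0.80 + 0.20(1 − q)], N_R = 175 × that denominator
- d = P_T − P_R; c = (1/N_T + 1/N_R)/2; se as in SAP 7.5.1
- P(equivalence) ≈ Φ[(0.20 − c + d)/se − 1.645]; the upper limit is not a constraint here.

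At q = 0: se = √(0.24/175 + 0.16/175) = 0.0478 and c = 0.0057. Then (0.20 − 0.0057 − 0.20)/0.0478 − 1.645 = −1.76, so P = 3.9%.

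At q = 0.20: d = 0.60/0.92 − 0.80/0.96 = 0.652 − 0.833 = −0.181, se = 0.0473 and c = 0.0061. The argument is −1.375, so P = 8.5%.

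| Failures dropped | d | Formula | Simulation |
|---|---|---|---|
| 0% | −0.200 | 3.9% | 3.8% |
| 5% | −0.196 | 4.7% | 4.6% |
| 7% | −0.194 | 5.0% | 5.0% |
| 10% | −0.191 | 5.6% | 5.6% |
| 20% | −0.181 | 8.5% | 8.5% |
| 30% | −0.169 | 13.1% | 13.3% |

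The simulation used one million trials per row. Ten percent of failures means 7 of 70 in the test arm and 3.5 of 35 in the reference arm.

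**4. If cures are dropped too.** With 10% of failures and 5% of cures dropped, false equivalence is 4.6%. With 10% of each it is 3.8%, the same as with no exclusions.

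**5. Direction.** For small q each rate rises by about q·p(1 − p). For a lower test rate, the difference shrinks only if P_T + P_R exceeds 1. That holds here but depends on the true rates.

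**6. Power, if the loss is random.** At an assumed 0.70 v 0.75 with 175 per arm, power is 91.6%. Dropping 5% or 10% of both arms gives 90.2% or 88.8%. Selective loss matters more than loss of numbers.

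**The case against.** **The operative rule may not be visible.** The PP definition, most of SAP section 6 and section 8.8 are blacked out, and the Appendix II logic is held elsewhere. A reader might infer that the plan has no time limit at all. The documents do not show that; they show only that no visible statement of the rule has one. This limits the claim but does not remove it, because a hidden limit would still conflict with the unqualified sentence in Protocol 5.8.

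**Some failures may be protected.** The SAP's Per-Protocol Population section excludes subjects who discontinue early for *other* reasons, which implies a category that stays in. Protocol 6.6 lets a worsened subject be discontinued as a treatment failure. Part of the selective loss may therefore be blocked already. Late-using cured subjects gain no evident protection.

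**Protocol 10.9 is consistent with its own endpoint.** The Protocol reads cure at the test-of-cure visit, with no 48 h cut-off. A reader might call 10.9 itself defective. It is not: the mismatch arises once the SAP shortens scoring but keeps the medication item.

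**Late use is not harmless for every endpoint.** Microbiological cure is read from stool at Visit 3 and tabulated on PP (SAP 4.1.2, 7.5.2). Protocol 4.3 bars antimicrobials during the study, and one taken after 48 h could change that result. This stands and narrows the fix.

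**The size is uncertain.** No document gives a rate of late use. Below about 7% of failures the nominal 5% is not exceeded, and equal loss of cures removes the inflation. This stands too.

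**Conclusion.** The point holds in a limited form. Read together, SAP 8.6 and Protocol 5.8 discard primary outcomes that SAP 4.1.1 has already fixed, and nothing visible explains why a subject may attend late and stay in PP yet be removed for a drug taken in that same late period.

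A reader might infer that the trial is biased toward equivalence. The documents do not support that. The direction assumes that late users are mainly failures and that the cure rates sum to more than 1; the size assumes 175 per arm and true cure of 0.60 v 0.80. On those assumptions false equivalence goes from about 3.8% with none dropped to 5.6% at 10% of failures and 8.5% at 20%. These are illustrations over a range, not estimates. The reason to act is that valid data are lost and the correction is cheap.

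**What to change.** Change the analysis set only; the prohibition and the withdrawal rule stay as they are.

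- In SAP 8.6, the PP sentence of Protocol 5.8 and the PP logic: for the primary clinical-cure analysis, limit this exclusion to prohibited-medication use up to the end of all primary scoring, that is, 48 h after the last dose or the end of Study Day 5 if later.
- List later use as a deviation, but keep the subject with the diary-scored outcome. State that withdrawal for such later use does not remove the subject through the early-discontinuation sentence of the PP definition.
- Keep the existing exclusion for the PP analysis of microbiological cure.
- Before unblinding, fix a conservative boundary rule: use on the boundary day without a clock time counts as inside the window.
- If the withheld PP logic already contains such a limit, state it in SAP 8.6 and Protocol 5.8.

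**Cost.** A few sentences, one comparison of medication dates with the last-dose time, and separate PP flags for the primary and microbiological analyses. Protocol 5.8 mentions the date and duration of concomitant medication but not clock time. Since the gap is at most 24 h inside the Protocol window, the boundary rule may decide many of the cases, and some already-scored subjects will still be lost.
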